4.6 Demographic and Other Baseline Characteristics

Age will be calculated as the number of complete years between a participant's birth date and the date of informed consent.

Demographic and other baseline characteristics will be listed for all participants and summarised for the Full Analysis Population, as:

- Demographics
 - age (years),
 - age group (< 50, ≥ 50 to < 65, ≥ 65 to < 85, ≥ 85 years),
 - sex, race (if collected),
 - country,
 - ethnicity.
- Participant characteristics at baseline
 - height [cm],
 - weight [kg],
 - weight groups (< 40, ≥ 40 - < 75, ≥ 75 - < 90, ≥ 90 - < 120, and ≥ 120 kg),
 - body mass index (BMI),
 - BMI groups: Underweight (<18.5 kg/m²), Normal weight (= 18.5 - < 25.0 kg/m²), Overweight (= 25.0 - < 30.0 kg/m²), Obese (≥ 30.0 kg/m²).
- Baseline disease characteristics
 - Type 2 Diabetes Mellitus (T2DM) diagnosis (Y/N)
 - T2DM duration (years),
 - CKD stage (eGFR category): Stage 2 (60–89 mL/min)/Stage 3a (45–59 mL/min)/Stage 3b (30–44 mL/min)/Stage 4 (15–29 mL/min)/Stage 5 (<15 mL/min),
 - eGFR (mL/min/1.73m²),
 - albuminuria (defined as 200 -5000 mg albumin/g creatinine; count and percentage of participants meeting criteria),
 - SGLT2i history (background/no background),
 - primary renal diagnosis: Cystic kidney disease, Diabetic nephropathy, Ischaemic/Hypertensive nephropathy, Chronic glomerulonephritis, Renal artery stenosis, Chronic pyelonephritis (infectious), Chronic interstitial nephritis, Obstructive nephropathy, Unknown, Other (Specify),
 - Chronic glomerulonephritis type: IgA nephropathy, Focal segmental glomerulosclerosis (FSGS), Lupus nephritis, Membranous nephropathy, Minimal change, Other primary or secondary glomerulonephritis,
 - Angiotensin Converting Enzyme Inhibitors (ACEi)/ Angiotensin II Receptor Blockers (ARB) history (Y/N)
- A summary and a list of participants by site and country will be provided.

Medical history and relevant surgical history will be coded using MedDRA version 23.0 or later. The frequency and percentage of participants with each condition will be summarised by System Organ Class (SOC) and preferred term (PT). Participants with multiple unique terms will be counted once per each unique PT and unique SOC. A participant can have one or more PTs reported under a given SOC. Each summary will be sorted alphabetically by SOC and PT, unless otherwise stated.

By-participant listings of demographic data (including age, sex, race, baseline weight, baseline height and baseline BMI) and the baseline disease characteristics data detailed above will be provided.

4.7 Concomitant Medication

Any medication or vaccine (including over-the-counter or prescription medications, vitamins, and/or herbal supplements) that the participant is receiving at the time of enrolment or receives during the study will be recorded as concomitant. Medications starting after the completion/withdrawal date of study will be listed but will not be classified or summarised.

If medication start and/or stop dates are missing or partial, the dates will be compared as far as possible with the date of enrollment. Medications will be assumed to be concomitant only, unless there is clear evidence (through comparison of partial dates) to suggest that the medication started prior to enrollment. If there is clear evidence to suggest that the medication started prior to enrollment, the medication will be assumed to be both prior and concomitant, unless there is clear evidence to suggest that the medication stopped prior to enrollment. If there is clear evidence to suggest that the medication stopped prior to enrollment, the medication will be assumed to be prior only.

The frequency and percentage of participants receiving rescue medication during the treatment periods will be presented by treatment group. A by-participant listing will also be presented for all rescue medications taken during the treatment periods, by treatment group.

Concomitant medications will be summarised by drug class and (generic) drug name. A summary table by drug class and generic drug name will be generated for each of the following:

- all allowed concomitant medication taken during the study
- disallowed concomitant medication taken during the study

The type of medication in terms of common concomitant, anti-diabetic, and heart failure related medication will be derived from the CRF module assigned to the respective type of medication. A by-participant listing of concomitant medications at study entry and taken during treatment will be presented.

A by-participant listing of medications not started due to the COVID-19 pandemic will be presented.

4.8 Treatment Compliance

Treatment compliance will be assessed using two methods:

- Counting the number of AZD5718/placebo and dapagliflozin tablets dispensed to and taken by each participant, providing an overall percentage of treatment compliance for the study.
- Summarising instances of dose interruptions lasting 3 or more consecutive days.

Participants will be requested to return all unused study medication and empty packages to the clinic at each visit. The amount of dispensed and returned study medication will be recorded in the eCRF. The percentage treatment compliance will be calculated from the dose as:

$$\frac{\text{Overall amount of dose actually taken}}{\text{Overall amount of dose planned}} \times 100$$

Participants taking $\geq 80\%$ and $\leq 120\%$ of planned study medication are considered to be compliant. Overall study compliance percentage will be summarised as follows:

- Descriptive statistics will be summarised by the four treatment groups and overall.
- Percent compliance will be categorised according to the following three categories:
 - $< 50\%$ or $\geq 150\%$ (significant drug non-compliance)
 - $\geq 50\%$ and $< 80\%$ or $> 120\%$ and $< 150\%$ (moderate drug non-compliance)
 - $\geq 80\%$, $\leq 120\%$ (drug compliance)

A by-participant listing of treatment compliance data will be provided.

A separate compliance measure is to be defined as dose interruptions which last three or more days. This will indicate severe non-compliance.

A summary of the number of occurrences of drug interruptions lasting three or more consecutive days, by treatment group and treatment period. A by-participant listing of all participants who have at least one instance of a dose interruption of three or more consecutive days will be presented.

4.9 Efficacy Evaluation

4.9.1 Analysis and Data Conventions

This study is designed to test for superiority and assess the dose-response relationship. The null hypothesis for the treatment comparison will be that there is no difference between AZD5718 with dapagliflozin and placebo with dapagliflozin on urine ACR. The alternative hypothesis will be that there is a difference. Symbolically, this is expressed as follows:

$$H(0): \mu(\text{AZD5718+dapagliflozin}) = \mu(\text{placebo} + \text{dapagliflozin})$$

$$H(1): \mu(\text{AZD5718+dapagliflozin}) \neq \mu(\text{placebo} + \text{dapagliflozin})$$

A 2-sided test with $\alpha = 0.1$ will be used to test this hypothesis.

4.9.1.1 Dose-response Testing

Not applicable for this study. See Section 4.14 for further details.

4.9.1.2 Multi-centre Studies

No per centre (where the term ‘centre’ defines each investigator site) summaries or analyses will be made.

4.9.1.3 Adjustments for Covariates

The primary efficacy analysis will be adjusted for the following baseline covariates:

1. DKD status (stratification variable)
2. SGLT2i history (stratification variable)
3. Visit
4. Baseline measure of log (urine albumin to creatinine ratio [UACR])
5. Treatment-by-visit interaction
6. Baseline log (UACR)-by visit interaction

Strata with low counts (<5 participants in a stratum) will be pooled with adjacent strata.

4.9.1.4 Handling of Dropouts or Missing Data

Summary statistics will be based on non-missing values. For analyses of UACR, if a measurement is missing it will not be imputed. Missing safety data will generally not be imputed. However, safety assessment values (vital signs, laboratory assessments excluding urine albumin, urine creatinine and UACR) of the form of “< x” (ie, below the lower limit of quantification) or > x (ie, above the upper limit of quantification) will be imputed as “x” in the calculation of summary statistics but displayed as “< x” or “> x” in the listings. Measurements of urine creatinine, urine albumin and UACR which are displayed as “< x” or “> x” will be imputed by Covance Central Laboratory in order to effectively calculate the geometric mean.

Partial or missing dates

If the start date of the concomitant medication, medical history relating to T2DM diagnosis or AE is missing, the following rules will be applied:

- If the year is missing, the year should be imputed as the year that participant received the first dose of study treatment.
- If the year is available and the month and day are missing, then impute the month as January and the day as 01.
- If the year and month are available and the day is missing, impute the day as 01 (the first day of the month).
- If any of the above puts the date before the date of first dose of study treatment, a conservative approach is followed and, the date is imputed using the date of first dose.

If the stop date of the concomitant medication or AE is missing, the following rules will be applied:

- If the year is missing, the year should be imputed as the year that participant received the last dose of study treatment.
- If the year is available and the month and day are missing, then impute the month as December and the day as 31.
- If the year and month are available and the day is missing, impute the day as the last day of the month (eg, 28, 29, 30, or 31).
- It is not expected to have missing dates for unscheduled laboratory or ECG data. However, if there are missing dates, for any derivations, the dates should be imputed following the rules for concomitant medications and AEs.

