6.5.1 Prohibited Concomitant Medications

Use of OTC medications, herbal supplements, vitamins, etc, from Screening through to the early discontinuation visit is discouraged. Participants must be instructed not to take any medications, including OTC products, without first consulting with the Investigator. Non-study SGLT2i or GLP1-RA should not be initiated after enrolment in the study.

Participants are not permitted to receive any of the following medications during the study.

- 1 Systemic (oral or injectable) corticosteroids within 28 days of Screening Visit 1 until the end of the Follow-up Period.
- 2 Any other immunosuppressive therapy within 3 months of randomisation until the end of the Follow-up Period.
- 3 Any immunotherapy within 3 months of randomisation, except for stable maintenance dose allergen-specific immunotherapy started 28 days prior to Screening Visit 1 until the end of Follow-up Period.
- 4 Interferon gamma within 3 months of randomisation until the end of the Follow-up Period.
- 5 Investigational products other than AZD5718 within 4 months or 5 half-lives of randomisation until the end of the Follow-up Period.
- 6 Immunoglobulin or blood products within 28 days of Screening Visit 1 until the end of the Follow-up Period.
- 7 Ongoing use of any biologic drug or small molecule targeting the immune system (for example, tumour necrosis factor blockers, anakinra, rituximab, abatacept, azathioprine, tocilizumab, mycophenolate, corticosteroids other than topical or inhaled).
- 8 Any serum creatinine-altering drugs within 1 month prior to Screening Visit 1 including but not limited to amphotericin, cimetidine, clofibrate, dronedarone, ketoconazole, probenecid, ranolazine, trimethoprim, cyclophosphamide, aminoglycosides, or cephalosporins until the end of the Follow-up Period.
- 9 Any medication that alters leukotriene levels or actions within 4 weeks of Screening Visit 1, eg, zileuton cilastatin, and montelukast until the end of the Follow-up Period.
- 10 Simvastatin, lovastatin, or atorvastatin at doses > 40 mg per day within 1 month of Screening Visit 1 until the end of the Follow-up Period.

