4.10.2 Adverse Events

Adverse events will be coded using MedDRA version 23.0 or later.

An AE (classified by preferred term) started during the treatment period will be considered a treatment-emergent adverse event if it was not present prior to the first dose of randomised treatment. An AE that starts more than 7 days after the last dose of study medication will not be counted as a treatment-emergent AE. AEs which worsen after the start of treatment will not be included as a treatment-emergent AE but will be recorded.

Adverse events (and also separately SAEs) will be summarised by study treatment group in incidence summaries by MedDRA SOC and PT. Adverse events will be assigned to the period where they start and will be summarised for the Safety Analysis Set, with selected outputs summarized for the Monotherapy Safety Analysis Set and Extended Safety Analysis Set with Week 12 flag. Serious adverse event collection will begin after the participant signs the informed consent document, and all AE collection will begin after the participant has received the first dose of the study drug. The SAE/AE collection will last until the end of the participant’s follow-up period.

All AEs will be listed and assigned to on/off treatment period as:

- Prior treatment: The SAE occurred before the first administration of study drug. Only applicable for SAEs.
- On treatment: The AE occurred on or after the first administration until 7 days after last dose of AZD5718 and/or dapagliflozin.
- Off treatment: The AE occurred more than 7 days after the last dose of study drug.

The number, percentage and percentage per participant exposure year (PEY) of participants reporting treatment-emergent AEs in each treatment group will be tabulated by SOC and PT; by SOC; by SOC, PT, and relationship to study medication as assessed by the Investigator. If more than one event occurs with the same preferred term for the same participant, the participant will be counted only once for that preferred term using the most severe and most related occurrence for the summarisation by severity and by relationship to the study medication.

The event rate per 100 PEY is defined as:

$$\left(\frac{\text{number of subjects with AE}}{\text{sum of days at risk for AE in treatment period} + 7 \text{ days}} \right) \times 365.25 \times 100$$

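### SAP 4.9.1.4 floors partial T2DM diagnosis and medication start dates at first dose, which understates T2DM duration and is inconsistent with SAP 4.7

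*SAP*

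**What the plan says.** SAP 4.9.1.4, under partial or missing dates, sets one rule for three kinds of start date: "If the start date of the concomitant medication, medical history relating to T2DM diagnosis or AE is missing, the following rules will be applied". The steps are:

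- **Year missing:** "If the year is missing, the year should be imputed as the year that participant received the first dose of study treatment".
- **Only the year known:** "If the year is available and the month and day are missing, then impute the month as January and the day as 01".
- **Year and month known:** the day becomes 01.
- **Floor:** "If any of the above puts the date before the date of first dose of study treatment, a conservative approach is followed". In that case first dose replaces the completed date.

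No exception is made for T2DM history, or for a partial date whose known part already shows a start before first dose.

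SAP 4.6 lists T2DM duration in years among the baseline disease characteristics, and by-participant listings of those characteristics are planned. It gives no reference date for the duration, although it does count age to informed consent.

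SAP 4.7 has a separate rule for classifying medications, which compares the partial date with enrolment: "If there is clear evidence to suggest that the medication started prior to enrollment, the medication will be assumed to be both prior and concomitant". The exception is a drug that clearly stopped before enrolment. Sections 4.7 and 4.9.1.4 do not refer to each other.

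**The concern.** Moving an uncertain onset to first dose is conservative for an adverse event, because it counts a doubtful event as on treatment. It is not conservative for disease history or background therapy, where the true start is before first dose by design. Protocol 5.1 requires a T2DM diagnosis for the DKD sub-group. It also requires ACE inhibitor or ARB dosing to be stable for at least 4 weeks before Screening Visit 1, except in participants who cannot tolerate these drugs. For such dates the floor discards the known year and substitutes a date that cannot be right.

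Two outputs are at stake. The first is the T2DM duration summary for a sub-group planned as 67% of participants. The second is the imputed start date of background medications, which can show Day 1 for a drug that SAP 4.7 calls prior and concomitant.

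**Working it through.** The plan gives no figure to reproduce, so the check applies the rule as written.

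**Inputs.** The completion steps and the floor come from SAP 4.9.1.4. The screening window, Day -32 to Day -3, comes from the Schedule of Activities. The 67% DKD share and 632 participants come from Protocol 4.1. The following are assumptions: a first dose on 15 June 2021, true mean T2DM durations of 10, 15 and 20 years, and the shares of partial dates.

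**Formula.** Let F be first dose and D the completed date.

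- Imputed start = later of D and F
- Years before first dose = (F − imputed start) / 365.25

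Example: T2DM recorded as 2006 gives D = 1 January 2006. Without the floor, the interval to 15 June 2021 is 5,644 days, and 5,644 / 365.25 = 15.45 years. With the floor, the start is 15 June 2021 and the duration is 0.00.

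| Recorded | Completed date | Date after floor | Years, no floor | Years, with floor |
|---|---|---|---|---|
| T2DM 2006 | 1 Jan 2006 | 15 Jun 2021 | 15.45 | 0.00 |
| T2DM Mar 2006 | 1 Mar 2006 | 15 Jun 2021 | 15.29 | 0.00 |
| T2DM 2020 | 1 Jan 2020 | 15 Jun 2021 | 1.45 | 0.00 |
| T2DM fully missing | 1 Jan 2021 | 15 Jun 2021 | 0.45 | 0.00 |
| T2DM September, year missing | 1 Sep 2021 | 1 Sep 2021 | −0.21 | −0.21 |
| Medication 2015 | 1 Jan 2015 | 15 Jun 2021 | 6.45 | 0.00 |
| Medication May 2021 | 1 May 2021 | 15 Jun 2021 | 0.12 | 0.00 |

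The result does not depend on the assumed first-dose date. For a year-only record up to the first-dose year, 1 January is never later than F, so the later of the two is always F. The same holds for any year-and-month record from an earlier year. First-dose dates of 1 January and 31 December 2021 gave the same outcome.

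**Reference date.** Zero is exact only if duration is counted to first dose. If it is counted to a consent or screening date between Day -32 and Day -3, it is about −32 / 365.25 = −0.09 to −3 / 365.25 = −0.01 years.

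**Effect on the summary.** If a share p of DKD participants have a known-year partial date and the same true mean M as the rest, the reported mean is M × (1 − p).

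| Assumed true mean | 5% partial | 10% partial | 20% partial |
|---|---|---|---|
| 10 years | 9.5 | 9.0 | 8.0 |
| 15 years | 14.25 | 13.5 | 12.0 |
| 20 years | 19.0 | 18.0 | 16.0 |

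The planned DKD group is 0.67 × 632 = 423, so 5% is about 21 participants and 20% about 85. If partial dates are more common in long-standing diabetes, the loss is larger than shown.

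**Medications, side by side.** Take a drug recorded as started in 2015. Under SAP 4.7 the known year is before enrolment, so the drug is prior and concomitant. Under SAP 4.9.1.4 the same record gets a start date of 15 June 2021. Label and date disagree.

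**The case against.** The strongest reply is that little depends on these dates, and most of it stands. T2DM duration is one descriptive item. It is not a covariate (SAP 4.9.1.3), a randomisation stratum or a sub-group (SAP 4.9.1.6). Complete dates are untouched, and the frequency of partial dates is unknown. Prior and concomitant status follows the partial date itself under SAP 4.7, and the medication tables are by drug class and generic name. What remains for medications is a wrong imputed start date and a missing cross-reference. None of this rescues the T2DM rule, which names diagnosis dates explicitly.

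A reader might infer two larger consequences.

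- **Effect on UACR.** Protocol 6.5.1 says "Non-study SGLT2i or GLP1-RA should not be initiated after enrolment in the study". A background SGLT2i or GLP1-RA floored to Day 1 could look like a new start, be treated as prohibited use, and set later UACR to missing. The documents do not show this. SAP 4.4.2 detects programmable deviations from data recorded in the clinical database and then has them reviewed. SAP Appendix D describes case-by-case review of important deviations. SGLT2i background is also held separately as a stratification factor. No section says that imputed dates drive a deviation or remove UACR data.
- **AEs in the wrong period.** SAP 4.10.2 says "Adverse events will be assigned to the period where they start", so an AE known only by the first-dose year would default to Day 1 and hence Treatment Period 1. That follows from the rule, but such records should be rare. Protocol 8.3.2 collects the date and time of AE start, and Protocol 8.3.4 has site staff ask about problems since the participant was last asked. The documents do not support a claim that the period tables would be materially distorted.

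**Conclusion.** The point holds as a narrow, low-severity error. As written, the rule gives about 0 years of T2DM duration for every DKD participant whose diagnosis date is partial with a known earlier year, and a small negative value if duration is counted to consent. A known month with a missing year can also give a negative duration. The planned summary is biased downward in proportion to the share of partial dates. The sizes shown rest on assumed means, assumed shares, and the assumption that participants with partial dates resemble the rest.

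Imputed start dates of background medications with a known pre-dose year or month are also wrong and disagree with SAP 4.7. The effect stays within the baseline summary, the listings and the imputed medication dates. Nothing in the documents carries it into UACR or the primary analysis.

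**What to change.** Amend SAP 4.9.1.4 and SAP 4.6 as follows.

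- **T2DM diagnosis:** exempt it from the floor. Complete the date within the known year or month. The existing 1 January and day 01 defaults would serve, and they overstate duration by less than a year or less than a month. Leave the date missing if the year is unknown.
- **Duration:** state the reference date in SAP 4.6, either informed consent (as for age) or first dose.
- **AE and medication start dates:** apply the floor only when the known parts are compatible with a start on or after first dose. In the example above, a medication recorded as 2021 or June 2021 would be floored to 15 June 2021, while one recorded as 2015 or May 2021 would keep its completed date. The condition matters for AEs too, because SAEs are collected from consent and SAP 4.10.2 has a prior-treatment category for them.
- **Cross-reference:** say in SAP 4.9.1.4 that SAP 4.7 governs prior and concomitant status.

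The cost is a few lines of SAP text and derivation code. No new data are needed.

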4.9.1.5 Interim Analyses

An administrative interim analysis will be conducted when approximately 211 participants have completed the 20-week treatment period. See Section 4.12 and [Appendix B](#) for further details

4.9.1.6 Examination of Sub-groups

Sub-group analyses for the primary efficacy endpoint by SGLT2i background and by DKD status will be presented. Summaries of the primary efficacy variable by treatment group and sub-group will also be produced. No formal statistical analysis will be performed within these sub-group.

A forest plot will present the least-squares mean and 90% CI overall and for each sub-group individually. These will be taken from the primary analysis model.

